5.3.1.3.2. Hospitalized Subjects only

Formulae to be used for derived clinical course parameters for the hospitalized subjects, are provided in [Table 20](#).

Table 20: Additional Clinical Course Parameters for Hospitalized Subjects

Measurement	Formula						
Time (hours) to hospital discharge [time to event]	
The time from treatment initiation to first hospital discharge (=event) in hours.
 
Censoring will be done as follows:
 
  
 Situation	Censoring	
   
 Missing information due to completion or withdrawal from study prior to the event	date of completion or withdrawal. If time is not available, the subject will be censored at 12:00.	
 
 Death (without previous discharge)	date/time of death	
  
 
time to event (hours) = (date/time of event or censoring – date/time of first dose of study drug)/3600, rounded to one decimal
	Situation	Censoring	Missing information due to completion or withdrawal from study prior to the event	date of completion or withdrawal. If time is not available, the subject will be censored at 12:00.	Death (without previous discharge)	date/time of death
Situation	Censoring						
Missing information due to completion or withdrawal from study prior to the event	date of completion or withdrawal. If time is not available, the subject will be censored at 12:00.						
Death (without previous discharge)	date/time of death						
Time (hours) to clinical stability: investigator assessment [time to event]	
The time from treatment initiation to first clinical stability (=event) in hours, with clinical stability evaluated by the investigator and captured in the Clinical Stability eCRF.
 
Censoring rules and derivation: as for 'Time (hours) to hospital discharge'
						
Time (hours) to hospital discharge since hospital admission [time to event]	
The time (hours) from hospital admission to first hospital discharge (=event) as captured in the Hospitalization (Inpatient) eCRF.
 
Derivation of censoring similar as "Time (hours) to hospital discharge".
						

Table 20: Additional Clinical Course Parameters for Hospitalized Subjects

	time to event (hours) = (date/time of event or censoring – date/time of hospital admission)/3600, rounded to one decimal
Time (hours) to clinical stability: investigator assessment since hospital admission [time to event]	
The time (hours) from hospital admission to first clinical stability (=event), as evaluated by the investigator and captured in the Clinical Stability eCRF.
 
Censoring rules and derivation: as for 'Time (hours) to hospital discharge'

Duration of need for intensive care unit (ICU) stay (hours) [duration]	
The total number of hours a subject experienced a medical need to stay in ICU (=event) from first dose of study drug until study termination, calculated as sum of [(end date/time of event – start date/time of event)/3600], rounded to one decimal for all separate events per subject as captured in the ICU eCRF. Based on the medical need to stay in ICU start/end date/time.
 
Where:
 
 • If the initial start date/time is prior to the first dose of study drug, the duration prior to the first dose of study drug will be deducted from the overall duration • If start date/time is missing, it will be imputed using date/time of first dose of study drug • If the end date is missing, the end date is considered to be after study completion or withdrawal • If the end date/time is after study completion/discontinuation, the duration after the date/time of study completion/discontinuation will be deducted from the overall duration (implies imputation of completion/discontinuation date/time) • If start date is available but the start time is not available, it will be imputed as 00:00 • If end date is available but end time is not available and: 
 ○ End date equals hospital discharge date, end time will be imputed as the hospital discharge time (only if hospital discharge time is also not an imputed time), else imputed as 23:59 (if hospital discharge time is also an imputed time) ○ End date does not equal hospital discharge date, end time will be imputed worst-case as 23:59
Actual duration of intensive care unit (ICU) stay (hours) [duration]	
For subjects in Cohort 1: total number of hours of actual ICU stay experienced by a subject from first dose of study drug until end of study (sum of the duration of individual ICU records captured in the Hospitalization [Inpatient] eCRF) and is derived as:
 
time hours = sum [(end date/time – start date/time [of encounter])]/3600
 
Derivation and imputation rules: as for 'Duration of need for intensive care unit (ICU) stay (hours)'

Table 20: Additional Clinical Course Parameters for Hospitalized Subjects

Need for ICU stay [binary]	
Was there a medical need for the subject to stay in the ICU after first dose of study drug? Categories will be Yes (1) or No (0).
 
Only derive this parameter for subjects that were not in ICU before first dose of study drug (no score will be assigned otherwise).

Duration of oxygen supplementation [duration]	
The total number of hours a subject used supplemental oxygen (=event) from first dose of study drug until study termination, calculated as sum of [(end date/time of event - start date/time of event)/3600], rounded to one decimal for all separate events per subject
 
Derivation and imputation rules: as for 'Duration of need for intensive care unit (ICU) stay (hours)'
 
If the subject required oxygen supplementation prior to the current respiratory infection, the end date/time will be the date/time that the supplemental oxygen administration returned to the level provided prior to the current respiratory infection.

Need for oxygen supplementation [binary]	
Does the subject require any oxygen supplementation (non-invasive or invasive) after first dose of study drug?
 
Categories will be Yes (1) or No (0).
 
Only derive this parameter for subjects that did not require oxygen supplementation before first dose of study drug (no score will be assigned otherwise).
 
If the subject required supplemental oxygen prior to the current respiratory infection, requirement will be defined as having not returned to the level provided prior to the current respiratory infection.

Requirement for non-invasive non-mechanical ventilation support [binary]	
Does the subject require non-invasive non-mechanical ventilation support after first dose of study drug? On the Oxygen Supplementation form, oxygen supplementation is indicated but the type of supplemental oxygen administration does not equal “Non-Invasive Mechanical Ventilation” or “Invasive Mechanical Ventilation”?
 
Categories will be Yes (1) or No (0).
 
Only derive this parameter for subjects that did not require non-invasive non-mechanical ventilation before first dose of study drug (no score will be assigned otherwise).

Requirement for non-invasive mechanical ventilation support [binary]	
Does the subject require non-invasive mechanical ventilation support after first dose of study drug, as indicated on the Oxygen Supplementation form: type of supplemental oxygen administration equals “Non-Invasive Mechanical Ventilation”?
 
Categories will be Yes (1) or No (0).
 
Only derive this parameter for subjects that did not require non-invasive mechanical ventilation support or invasive mechanical

Table 20: Additional Clinical Course Parameters for Hospitalized Subjects

	ventilation support before first dose of study drug (no score will be assigned otherwise).
Requirement for invasive mechanical ventilation support [binary]	Does the subject require invasive mechanical ventilation support after first dose of study drug, as indicated on the Oxygen Supplementation form: type of supplemental oxygen administration equals “Invasive Mechanical Ventilation”? Categories will be Yes (1) or No (0). Only derive this parameter for subjects that did not require invasive mechanical ventilation support before first dose of study drug (no score will be assigned otherwise).
Requirement for supplemental feeding/hydration [binary]	Does the subject require supplemental feeding/hydration (e.g. IV catheter/nasogastric tube) after first dose of study drug? Categories will be Yes (1) or No (0). Only derive this parameter for subjects that didn't require supplemental feeding/hydration before first dose of study drug (no score will be assigned otherwise). If the subject required supplemental feeding/hydration prior to the current respiratory infection, requirement will be defined as having not returned to the level provided prior to the current respiratory infection.
Duration of supplemental hydration/feeding (hours) [duration]	Total number of hours of hydration/feeding support experienced from first dose of study drug until end of study (sum of the duration of individual hydration/feeding administration records captured in the Feeding/Supplemental Feeding eCRF) and is derived as: $\text{time hours} = \text{sum} [(\text{end date/time} - \text{start date/time}) \text{ [of encounter]}] / 3600$ Derivation and imputation rules: as for 'Duration of need for intensive care unit (ICU) stay (hours)'
Time (hours) to end of oxygen supplementation up to 72h from first hospital discharge [time to event]	Regardless of whether or not the subject is receiving oxygen supplementation at time of first dose of study drug: time (hours) from first dose of study drug to last end date/time of any oxygen supplementation received, but within 72h following first hospital discharge. Excludes oxygen supplementation received during re-hospitalizations that occurred >72 hours after initial hospital discharge Time (hours) will be set to 0h for subjects not requiring oxygen supplementation after first dose of study drug. Censoring will be applied as follows:

Situation**Censoring**

Table 20: Additional Clinical Course Parameters for Hospitalized Subjects

	
For subjects with missing data prior to event due to:
 
 • Completion • Withdrawal/early discontinuation of the study • Lost to follow-up (LTFU) 
Death (without previous evidence of supplementation end/hospital discharge)
	
Censored at date/time of completion, withdrawal/discontinuation of the study or LTFU accordingly Note: missing time will be imputed as 12:00
 
Censored at date/time of death
				
		time to event (hours) = (date/time of event or censoring – date/time of first dose of study drug)/3600, rounded to one decimal				
Time (hours) to end of hydration/feeding supplementation up to 72h from first hospital discharge [time to event]	
Regardless of whether or not the subject is receiving hydration/feeding supplementation at time of first dose of study drug: time (hours) from first dose of study drug to last end date/time of any hydration/feeding supplementation received, but within 72h following first hospital discharge. Excludes hydration/feeding supplementation received during re-hospitalizations that occurred >72 hours after initial hospital discharge
 
Time (hours) will be set to 0h for subjects not requiring hydration/feeding supplementation after first dose of study drug.
 
Censoring will be applied as follows:
	
Situation
 
 
 For subjects with missing data prior to event due to:	Censored at date/time of completion, withdrawal/discontinuation of the study or LTFU accordingly Note: missing time will be imputed as 12:00	
 
 Death (without previous evidence of supplementation end/hospital discharge)	Censored at date/time of death	
 
 
time to event (hours) = (date/time of event or censoring – date/time of first dose of study drug)/3600, rounded to one decimal
	For subjects with missing data prior to event due to:	Censored at date/time of completion, withdrawal/discontinuation of the study or LTFU accordingly Note: missing time will be imputed as 12:00	Death (without previous evidence of supplementation end/hospital discharge)	Censored at date/time of death
For subjects with missing data prior to event due to:	Censored at date/time of completion, withdrawal/discontinuation of the study or LTFU accordingly Note: missing time will be imputed as 12:00					
Death (without previous evidence of supplementation end/hospital discharge)	Censored at date/time of death					
Time (hours) to end of supplementation (oxygen and/or feeding/hydration) up to 72h from first hospital discharge [time to event]	
Time (hours) from first dose of study drug until the maximum date/time of supplementation end (oxygen- and/or hydration/feeding) and excluding supplementation received during re-hospitalizations that occurred >72 hours after initial hospital discharge.
 
Time (hours) will be set to 0h for subjects not requiring supplementation (oxygen- and/or hydration/feeding) after first dose of study drug.
 
In case either of the two components are censored, the time to actual end of supplementation (oxygen and/or hydration/feeding)
					

Table 20: Additional Clinical Course Parameters for Hospitalized Subjects

	
will also be censored at the last timepoint of the censored component.
 
time to event (hours) = (maximum (date/time of event or censoring) – date/time of first dose of study drug)/3600, rounded to one decimal

Time (hours) to return to pre-RSV disease level for RR: based on investigator evaluation [time to event]
	
The time (hours) from first dose of study drug until the date/time to return to pre-RSV disease level. The return to pre-RSV disease level occurs when the observed value of the parameter is indicated by the investigator as normal, and no later observed values are indicated by the investigator as abnormal (=event).
 
Normalization of RR will be derived from the investigator response to the corresponding question in the Vital Signs eCRF: 'Is this RR value normal for this patient?'
 
If no deterioration from pre-RSV disease levels occurred, the time will be set to time of first dose of study drug and the value will be set to 0 hours.
 
Subjects with an abnormal value at the last assessment will be censored at that time. Subjects for which this last assessment is the baseline assessment will be censored at time 0 hours.
 
time to event (hours) = (date/time of event or censoring – date/time of first dose of study drug)/3600, rounded to one decimal


Time (hours) to return to pre-RSV disease level for HR: based on investigator evaluation [time to event]
	
Censoring rules and derivation: as for 'Time to return to pre-RSV disease level for RR: based on investigator evaluation'
 
Normalization of HR will be derived from the investigator response to the corresponding question in the Vital Signs eCRF: 'Is this Pulse value normal for this patient?'

Time (hours) to SpO₂ ≥ 92% on room air [time to event]
	
The time from first dose of study drug until the time of first SpO₂ measurement ≥ 92% on room air, and where no supplemental oxygen supplementation is given at or after this timepoint and where no value < 92% are measured after this timepoint.
 
Subjects with SpO₂<92% on room air or who are still on oxygen supplementation at the last SpO₂ assessment will be censored at the date and time of the last SpO₂ assessment.
 
If no oxygen supplementation was necessary post-baseline and the subject had SpO₂ measurement ≥ 92% on room air at baseline and all post-baseline measurements, the value (time to event [hours]) will be set to 0 hours.
 
If the subject required supplemental oxygen prior to the current respiratory infection, end date/time will be defined as the date/time the subject has returned to the level provided prior to the current respiratory infection.
 
time to event (hours) = (date/time of event or censoring – date/time of first dose of study drug)/3600, rounded to one decimal

Table 20: Additional Clinical Course Parameters for Hospitalized Subjects

Time (hours) to $\text{SpO}_2 \geq 95\%$ on room air [time to event]	Censoring rules and derivation: as for 'Time (hours) to $\text{SpO}_2 \geq 92\%$ on room air'
Time (hours) to clinical stability: protocol definition [time to event]	
Time at which all the following criteria are met:
 
Return to pre-RSV disease status for otherwise healthy subjects and subjects with (a) risk factor(s) for severe RSV disease:
 
 • heart rate AND • respiratory rate AND • blood oxygen level 
AND
 
No more oxygen supplementation for otherwise healthy subjects and subjects with (a) risk factor(s) for severe RSV disease
 
AND
 
No more intravenous (IV)/nasogastric tube feeding/hydration in otherwise healthy subjects or return to pre-RSV status of IV/nasogastric tube feeding/hydration in subjects with (a) risk factor(s) for severe RSV disease
 
Time to clinical stability (protocol definition) will be evaluated using two approaches:
 
The time from first dose of study drug until the time at which each of the following criteria are met (=event):
 
 • Normalization of oxygen supplementation (as in parameter Time [hours] to end of oxygen supplementation up to 72h from first hospital discharge), • Normalization of feeding/hydration (as in parameter Time [hours] to end of hydration/feeding supplementation up to 72h from first hospital discharge), • Normalization of RR (as in parameter Time [hours] to return to pre-RSV disease level for RR: based on investigator evaluation), and • Normalization of HR (as in parameter Time [hours] to return to pre-RSV disease level for HR: based on investigator evaluation), and • Normalization of blood oxygen level (as in parameter Time [hours] to $\text{SpO}_2 \geq 92\%$ on room air) 
The time from first dose of study drug until the time at which each of the following criteria are met (=event):

Table 20: Additional Clinical Course Parameters for Hospitalized Subjects

	
 Normalization of oxygen supplementation (as in parameter Time [hours] to end of oxygen supplementation up to 72h from first hospital discharge), Normalization of feeding/hydration (as in parameter Time [hours] to end of hydration/feeding supplementation up to 72h from first hospital discharge), Normalization of RR (as in parameter Time [hours] to return to pre-RSV disease level for RR: based on investigator evaluation), and Normalization of HR (as in parameter Time [hours] to return to pre-RSV disease level for HR: based on investigator evaluation), and Normalization of blood oxygen level (as in parameter Time [hours] to $\text{SpO}_2 \geq 95\%$ on room air) 
In case any of the five components are censored, the time to clinical stability (protocol definition) will also be censored at the last timepoint of the censored component.
 
time to event (hours) = (maximum (date/time of event criteria or censoring) – date/time of first dose of study drug)/3600, rounded to one decimal

Need for re-hospitalization [categorical]	
If, after being discharged from the hospital (initial hospital discharge), subject is re-hospitalized (ward or ICU [inpatient status]) due to respiratory or other reasons. Re-hospitalization status will be categorized as:
 
 Yes 
 Hospital admission date/time at least 24 hours after initial hospital discharge date/time AND Reason for re-hospitalization, as assessed by the investigator, indicated on Medical Encounters [Inpatient/Outpatient] eCRF as: 
 AE Other 
If reason for re-hospitalization is indicated as AE, further differentiation will be made as follows:
 
 Respiratory AEs: 
 RSV-related complications: modified definition as detailed in Section 5.4 Other respiratory AEs Non-respiratory AEs 
This variable is only derived for those subjects who are re-hospitalized

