5.3.1.5. Medical Resource Utilization

Medical resource utilization will be assessed by the number, frequency and type of medical care encounters, including for RSV infection or RSV-related complications, based on investigator assessment.

Summary information will be provided as follows:

- Number of medical care encounters and reason (AE, Other)
- Type of medical care encounters such as medical practitioner office, emergency room, intensive care unit, home care, amongst others
- Type of practitioner
- Frequency of visits

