	
 • Not resolved: if ANY of the key RSV symptoms (concepts) scored >1 on study day of assessment Where the worst (highest) assessment collected per study day is considered. **Mechanical ventilation includes both invasive and non-invasive mechanical ventilation. 
RSV Recovery Scale: Definitions
 
Note: hospital discharge status as based on investigator evaluation captured in the Inpatient/Outpatient Status- and/or Hospitalization [Inpatient] eCRFs
 
1. Home without symptoms:
 
 • Discharged from hospital prior to study day of assessment AND • Without symptoms: based on the key RSV symptoms (concepts): ObsRO on study day of assessment 
2. Home with symptoms
 
 • Discharged from hospital prior to study day of assessment AND • With symptoms: based on the key RSV symptoms (concepts): ObsRO on study day of assessment 
3. Ward, not requiring supplementation (feeding/hydration and/or oxygen supplementation)
 
 • In non-ICU (ward) on study day of assessment (including re-hospitalization as captured in Medical Encounters [Inpatient/Outpatient] eCRF) and neither supplemental oxygen nor supplemental hydration/feeding is required by subject 
4. Ward), requiring supplementation (feeding/hydration and/or oxygen supplementation)
 
 • In ward on study day of assessment (including re-hospitalization as captured in Medical Encounters [Inpatient/Outpatient] eCRF) and supplemental oxygen and/or supplemental hydration/feeding is required by subject 
5. ICU, not requiring mechanical ventilation
 
 • ICU level of care is required at any time during the study day of assessment AND • Invasive or non-invasive mechanical ventilation not required by subject on study day of assessment 
6. Requiring mechanical ventilation
 
 • Any invasive or non-invasive mechanical ventilation on study day of assessment 
7. Death
 
 • Subject died prior to- or on study day of assessment (all-cause mortality) 
RSV Recovery Scale: ObsRO Imputation
 
In case of missing ObsRO assessments following hospital discharge, the worst-case scenario of the two home categories of the RRS will be selected, i.e. 'Home with Symptoms' and imputed as subject's assessment of RRS for that study day.

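### A missing ICU end date runs the ICU stay to study completion with no cap at hospital discharge, so a child already home can be credited with impossible ICU hours

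*SAP*

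**What the plan says.** Table 20 in SAP Section 5.3.1.3.2 defines two ICU durations for hospitalized children.

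- **Duration of need for ICU** adds up hours "for all separate events per subject as captured in the ICU eCRF", over the window "from first dose of study drug until study termination".
- **Actual duration of ICU stay** runs to end of study and is the "sum of the duration of individual ICU records captured in the Hospitalization [Inpatient] eCRF". It takes over the derivation and imputation rules of the first parameter.

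Three of those rules matter here. On a missing end date: "If the end date is missing, the end date is considered to be after study completion or withdrawal". On an end beyond the study: "the duration after the date/time of study completion/discontinuation will be deducted from the overall duration". On a known end date with no end time: "End date equals hospital discharge date, end time will be imputed as the hospital discharge time", provided that the discharge time is not itself imputed.

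Section 5 lists need for and duration of ICU stay as a secondary endpoint in hospitalized subjects. It describes need as being on the ICU, or on the hospital ward while judged to require ICU care. Section 5.3.2.3.2 restricts the reporting of derived durations to descriptive summaries.

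On re-admission, the ward categories of the RSV Recovery Scale (Section 5.4.1, Table 22) are defined as "including re-hospitalization as captured in Medical Encounters [Inpatient/Outpatient] eCRF". The re-hospitalization parameter in Table 20 takes the reason for re-admission from the same form.

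**The concern.** Taken together, the first two rules make an open ICU record last until the child leaves the study. Nothing in the list stops it at discharge, although the discharge date and time are already inputs to the derivation. A child sent home in the first week whose ICU end date was never entered would be recorded as in intensive care, or needing it, through the whole follow-up period.

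That is not a cautious upper bound. Under Section 5 the child must be in hospital to count as needing ICU care, so hours after discharge cannot exist for either parameter. If few children use the ICU, one such record can dominate the summary of an arm. The direction of the distortion depends only on the arm in which the date is missing.

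There is also a question of source for actual ICU stay. Its window runs to end of study, but the form named as its source is not the form that the SAP cites for re-hospitalization.

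**Working it through.** The SAP gives no target or expected value for ICU hours, so there is no figure to reproduce. The check applies the Table 20 rules to a single record.

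**Inputs from the SAP (Section 1.2 and Figure 1 notes):** discharge is possible from Day 2; follow-up ends on Day 28 ± 3, that is Day 25 to 31; Cohort 1 has 48 children per arm.

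**Assumptions:** discharge on Day 2, 3, 5 or 8; ICU start, discharge and completion at the same clock time; end date missing.

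**Formula.** Let S, D and C be the days of ICU start, discharge and completion.

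- Hours under the rule = (C − S) × 24
- Most hours possible in that admission = (D − S) × 24
- Excess = (C − D) × 24

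The start day cancels, so the excess does not depend on when the child entered the ICU.

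**Example, D = 5 and C = 28.**

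- ICU from first dose (S = 1): 27 × 24 = 648 h recorded, at most 4 × 24 = 96 h possible, excess 552 h.
- ICU entered on Day 3 (S = 3): 25 × 24 = 600 h recorded, at most 2 × 24 = 48 h possible, excess again 552 h.

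**Range of the excess (hours).**

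| Completion | Discharge Day 2 | Day 3 | Day 5 | Day 8 |
|---|---|---|---|---|
| Day 25 | 552 | 528 | 480 | 408 |
| Day 28 | 624 | 600 | 552 | 480 |
| Day 31 | 696 | 672 | 624 | 552 |

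These are lower bounds on the error, because the child may have left the ICU before discharge.

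**Effect on a mean.** This depends on a denominator that Table 20 does not state. If all 48 children in an arm count, with non-ICU children at 0 h, one record with the 552 h excess moves the mean by 552 / 48 = 11.5 h. If only ICU users count, and there are 10 of them (assumed), it moves by 552 / 10 = 55.2 h.

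**Source forms for re-admission, side by side.**

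| Item | Window | Form named |
|---|---|---|
| Need for ICU (Table 20) | To study termination | ICU eCRF, all events |
| Actual ICU stay (Table 20) | To end of study | Hospitalization [Inpatient] |
| Reason for re-hospitalization (Table 20) | After first discharge | Medical Encounters |
| Recovery Scale, ward categories (Table 22) | Day 1 to Day 8 | Medical Encounters |
| Recovery Scale, ICU category (Table 22) | Day 1 to Day 8 | None |
| Medical resource utilization (Section 5.3.1.5) | Not stated | None |

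The last row refers to "Type of medical care encounters such as medical practitioner office, emergency room, intensive care unit, home care, amongst others", so intensive care is an encounter type, but no form is tied to it. The table shows a possible mismatch for actual ICU stay. It does not show that re-admission ICU records are missing from the Hospitalization form.

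**The case against.** The rule is stated openly, applies equally to all arms, and treats an open record as ongoing, in line with the worst-case choice made elsewhere in the list for missing end times. It operates only when the whole end date is missing, and nothing in the SAP says how often that will be. The durations are descriptive, are not among the three key clinical course endpoints, and enter no interim decision rule. These limits on the consequence stand. The worst-case defence does not: a worst case must be possible, and ICU hours at home are not.

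The 648 h example can also be challenged. Section 5.3.2.3.2 words its ICU summary as covering children who did not need that care at first dose, so a child in ICU from first dose would fall outside it. That is fair for the 648 h total, but not for the 552 h excess, which is the same for a child who enters the ICU later. The 11.5 h shift is conditional on the denominator, as stated in the working.

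A reader might go further and infer that ICU stays in re-admissions are left out, so that ICU hours are wrong in both directions. The SAP does not support that. Duration of need takes every ICU eCRF event to study termination and excludes none. For actual ICU stay, omission is only an inference from form names: the eCRFs are not shown, the formula refers to encounters, and no exclusion is written. Re-hospitalizations are in any case tabulated, with individual profiles, under Section 5.3.2.3.2.

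**Conclusion.** The point holds for the missing end date. As written, both ICU durations run an open record to study completion or withdrawal with no cap at discharge, and the resulting hours are impossible under the SAP's own description of ICU need. The excess is 552 h per record for discharge on Day 5 and completion on Day 28, and 408 to 696 h over the range examined. The discharge days are assumptions, and the number of records affected is unknown. The harm is confined to descriptive summaries of a secondary endpoint in Cohort 1; no test or decision rule is touched.

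For re-admissions the finding is only that the source of actual ICU stay needs confirming. No undercount is established.

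**What to change.** In Table 20, for duration of need for ICU and actual duration of ICU stay, replace the missing-end-date rule: impute the earliest of the hospital discharge date/time of that admission, death, and study completion or withdrawal. Keep the change specific to the ICU parameters. The oxygen and feeding/hydration durations borrow the same rules, but the SAP allows for such support after discharge, so a discharge cap does not carry over automatically.

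For actual ICU stay, add a sentence confirming that ICU records from re-admissions are included, naming the form or forms that hold them, and stating that each stay is counted once. Simply adding up both forms could double count a stay recorded on each.

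The cost is two sentences and minor programming. The discharge date and time are already used in this derivation, so no new data are needed.
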